3.6.1. Assessment of Pain

Measurements of this outcome will consider pain intensity based on Figure 3-1. Preoperative and postoperative pain intensity will be assessed using a standardized 10-centimeter visual analogue scale (VAS), ranging from 0 (no pain) to 10 (worst possible pain) (Sirintawat et al., 2017). Prior to surgery, patients will receive thorough instructions on using the VAS to accurately self-report their pain. Following the procedure, they will record their pain scores on a standardized form and return it to the researcher on the day of suture removal, allowing for continuous monitoring and evaluation of pain management effectiveness (Costa et al., 2015).

[figure not shown]

Figure 3-1 Pain Intensity Measurement.

3.6.2. Assessment of Mouth Opening (Trismus)

Measurements of this outcome will be via comparing the difference in maximum mouth opening ability (MMOA) before and after surgery (Figure 3-2). This will be achieved by using a calibrated ruler to measure the distance between the upper and lower central incisors in millimeters, both preoperatively (baseline) and at defined post-operative time points. This approach allows for a quantifiable assessment of trismus development and recovery following the intervention (Sreesha et al., 2020).

Figure 3-2 Trismus Measurement - MMOA.

3.6.3. Assessment of Facial Swelling (Edema)

This outcome will be evaluated through using the method described by (Schultze-Mosgau et al., 1995) to quantify facial swelling pre- and post-operatively. Measurements will be taken with a flexible scale in the closed mouth position by marking five fixed points and three surgical base lines connecting the said fixed points as follows:

- 5 fixed points (F1 – tragus of ear, F2 – angle of mandible, F3 – soft tissue pogonion, F4 – Corner of mouth, F5 – lateral canthus of eye)
- 3 surgical base lines (S1 – from tragus of ear to corner of mouth, S2 – from tragus of ear to soft tissue pogonion, S3 – from lateral canthus of eye to angle of mandible).

[figure not shown]

Figure 3-3 Swelling Measurement.

3.7. Surgical Procedures

To minimize variability and bias, all surgical extractions will be performed by the same oral surgeon utilizing a uniform technique (Isola et al., 2019). Each patient will receive similar operative procedures under identical conditions, including administration of local anesthetic consisting of inferior alveolar, lingual, and long buccal nerve blocks. Additionally, the same surgical procedure will be adopted for all groups. Access to the third molar will be achieved from the buccal aspect. A mucoperiosteal flap will be raised, and bone removal with a round bur in a straight handpiece under continuous irrigation with a sterile saline solution and/or tooth sectioning will be performed. After tooth extraction, the alveolus will be inspected, curetted for granulation tissue removal, and irrigated with a sterile saline solution. The surgical wound will be closed using a 4–0 reabsorbable suture (Coated VICRYL). This meticulous approach minimizes intraoperative trauma and ensures consistency across all groups.

Post-operatively, patients will receive their assigned medications and receive thorough instructions regarding dietary restrictions (liquid and cold diet for 24 hours), oral hygiene practices, and avoidance of mouthwashes to prevent bleeding. They will be informed about potential complications and instructed to contact the surgeon if any issues arise. Additionally, they will be requested to report any physical symptoms experienced during the study period.

3.8.Ethical Consideration

The ethical approval will be obtained from the USTY Medical Research Ethics Committee. The purpose and methodology of the study will be explained to all the participants. Hence, a participant information sheet (Appendix B) will be given to all participants and a written informed consent form (Appendix C) will be obtained from them with the tenets of the revised Declaration of Helsinki 1975.

3.9.Statistical Method

Quantitative data (pain, trismus, and facial swelling) will be expressed as means and standard deviations and compared using the paired t test (parametric) or Wilcoxon test (nonparametric). The Shapiro–Wilk test will be used to verify the normality of the data. A difference of $P < .05$ will be considered statistically significant. The data analysis will be performed using SPSS V.25 (SPSS, JASP).

References

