In contrast, for many years, many phytotherapeutic drugs have been widely used for the treatment of inflammatory diseases and postsurgical conditions (Olmedo-Gaya et al., 2016; Pavan et al., 2012). There were favorable effects in the inflammatory parameters, when the phytotherapeutic drugs were used as a post-operative therapy of third molar surgery. The phytotherapeutic drug as a mixture of herbal extract with anti-inflammatory activity was shown to be safe and simple in the control of pain and control postsurgical discomfort after surgical removal of the third molar. Further studies are needed to understand better the role and potential benefits of phytotherapeutic drugs in the therapy after the removal impacted third molar (Isola et al., 2019). Escin is a natural molecule with a major active component of *Aesculus hippocastanum*. It is a natural mixture of triterpene saponins and has shown clinically considerable anti-inflammatory activity postoperatively and in traumatic injuries (Wang et al., 2009).

Based on the research gaps recommend by (Al-Khateeb & Nusair, 2008; Chopra et al., 2009; Mouneshkumar et al., 2015) to assess the efficacy of serratiopeptidase after third molar extraction and (Isola et al., 2019) to understand potential benefits of escin after the removal impacted third molar, the study aims at finding solid answers to the following main questions:

1. Does serratiopeptidase, when used in addition to conventional drugs, offer greater efficacy in reducing post-operative pain, trismus, and facial swelling compared to conventional drugs alone following impacted third molar surgery?
2. Does escin, when used in addition to conventional drugs, offer greater efficacy in reducing post-operative pain, trismus, and facial swelling compared to conventional drugs alone following impacted third molar surgery?
3. When both serratiopeptidase and escin are used in addition to conventional drugs following impacted third molar surgery, which one demonstrates superior efficacy in reducing post-operative pain, trismus, and facial swelling?

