The sample size is the number of participants planned to be included in the trial, usually determined using a statistical power calculation (Zanatta et al., 2017). This study determined the sample size using a power calculation based on previous research by (Costa et al., 2015). Their study found that preemptive use of etoricoxib 120mg significantly reduced the need for rescue analgesic medication compared to a placebo (1.6 ± 1.3 vs 4.0 ± 2.5). To achieve a power of 80% and a confidence interval of 95%. The study will need to evaluate 11 surgical sites per sub-group (<http://www.openepi.com/SampleSize/SSMean.htm>). To account for a potential 20% drop-out rate, a total of 14 sites per sub-group will be recruited. This will result in a total sample size of 56 dental units (2 teeth per patient) from 28 patients. The following Table 3-1 illustrates the study sample size and the planned treatment.

Table 3-1 : Sample Size and Study Treatment.

Groups	I		II		Total
Patients	14		14		28
Sub-groups	Control 1	Study 1	Control 2	Study 2	4
Sample size	14	14	14	14	56
Conventional Treatment	Amoxicillin 500mg Cap b.i.d		Metronidazole 500mg Tab t.i.d		N/A
	Diclofenac sodium 50mg Tab b.i.d				
Study Treatment	N/A	Serratiopeptidase 10mg t.id	N/A	Escin 20mg t.id	N/A

3.4.Sample Selection

Patients who will undergo to surgical removal of the impacted third molar will be assessed for their eligibility to participate according to the following inclusion and exclusion criteria:

Inclusion criteria:

- Medically fit patients.
- The presence of two asymptomatic mandibular third molar indicated for surgical extraction.
- Absence of pericoronitis or signs of inflammation during the last 30 days

Exclusion criteria:

- Patient administered other drugs such as NSAIDS and steroids.
- Patient has allergy to the drugs used in this study.
- Pregnant patient or a patient with lactation.
- Immunocompromised patients with diabetic or hypertension (from patient's history).
- Patients with irradiated maxillofacial region.
- Intellectually disabled patients and patients unable to come for follow up visits.
- Patients with acute and subacute pericoronitis

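### Section 3.9 plans no estimate or 95% CI for the within-patient difference, and names no analysis that can compare serratiopeptidase with escin

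*Combined protocol and SAP*

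**What the plan says.** Section 3.9 is the only statistical text. It states: "Quantitative data (pain, trismus, and facial swelling) will be expressed as means and standard deviations and compared using the paired t test (parametric"), with a Wilcoxon test as the nonparametric option. Shapiro–Wilk checks normality, and a difference at P < .05 "will be considered statistically significant". The section does not mention a within-patient difference, its SD, a confidence interval or an exact P value.

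A confidence interval appears once, in section 3.3: "To achieve a power of 80% and a confidence interval of 95" per cent. There it sets the confidence level of the sample-size calculation and is not a commitment to report an interval.

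The third question in section 1.2 asks, of the two add-on drugs, "which one demonstrates superior efficacy in reducing post-operative pain, trismus, and facial swelling". The general objective (section 1.4) and hypothesis 3 (section 1.5) make the same comparison. Under section 3.1 and Table 3-1, group I (14 patients) has one session with serratiopeptidase and one control session. Group II (14 other patients) has one session with escin and one control session.

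On numbers, section 3.3 says "The study will need to evaluate 11 surgical sites per sub-group" and "To account for a potential 20% drop-out rate, a total of 14 sites per sub-group will be recruited".

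**The concern.** There are two gaps.

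The first is in reporting. Each patient is their own control, so the effect is a within-patient difference and its precision depends on the SD of that difference. The SDs of the test and control sessions do not determine it, because the within-patient correlation also enters. A table of session means and SDs with a significance verdict does not show how precise the result is. With so few pairs, that matters most when the result is not significant.

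The second is in the analysis. The tests named in section 3.9 are paired. They suit hypotheses 1 and 2, where the same patient supplies both values. Hypothesis 3 compares different patients, so there are no pairs to form. The comparison stated as the overall purpose of the study therefore has neither a planned test nor a planned estimate.

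**Working it through.** **Inputs.** From section 3.3: 11 evaluable and 14 recruited sites per sub-group, which means 11 to 14 pairs per drug group. The sizing rests on a cited trial in which etoricoxib "significantly reduced the need for rescue analgesic medication compared to a placebo (1.6 ± 1.3 vs 4.0 ± 2.5"). Assumed, because the documents do not say: two-sided 5% testing, and a within-patient correlation ρ, shown from 0 to 0.9.

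**1. The plan's own figure.** Difference 4.0 − 1.6 = 2.4; summed variances 1.3² + 2.5² = 7.94.
- n = 7.94 × (1.960 + 0.842)² / 2.4² = 10.82, rounded up to 11. A one-sided test would give 9.
- 11 / (1 − 0.20) = 13.75, rounded up to 14.

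Both stated numbers reproduce. The calculation concerns active against placebo on rescue analgesia. It does not address drug versus drug.

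**2. What session SDs alone tell a reader.** SD of the difference = √(s₁² + s₂² − 2ρs₁s₂); half-width = t(0.975, n−1) × SD of the difference / √n. The SDs 1.3 and 2.5 serve only as illustration, since they belong to another outcome.

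| ρ (assumed) | SD of difference | Half-width, 11 pairs | Half-width, 14 pairs |
|---|---|---|---|
| 0 | 2.818 | ±1.893 | ±1.627 |
| 0.5 | 2.166 | ±1.455 | ±1.250 |
| 0.9 | 1.446 | ±0.971 | ±0.835 |

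At 14 pairs the same two SDs fit about a twofold range of precision (1.627 / 0.835 = 1.95).

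**3. When the interval can be recovered.** With complete pairs, the difference of the two means equals the mean within-patient difference, and SE = |difference| / t(P). In one simulated set of 14 pairs (SDs as above, ρ = 0.5) the mean difference was −0.960, with a true 95% CI of −1.963 to 0.043.
- From the means and P = .059: −1.962 to 0.042.
- From the means and P = .06: −1.967 to 0.047.

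Recovery fails if P is given only as below .05 or not significant, if Wilcoxon is used, if the difference is near zero, or if the means include patients with one session only.

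**4. Precision in SD units.**
- Within patient, t(0.975, n−1)/√n: 2.228/√11 = 0.672; 2.160/√14 = 0.577.
- Drug versus drug, t(0.975, 2n−2) × √(2/n): 2.086 × 0.426 = 0.889 with 11 per group; 2.056 × 0.378 = 0.777 with 14 per group.

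**5. What P ≥ .05 leaves open.** By the noncentral t distribution, power for a true paired effect of 0.5 SD is 32% with 11 pairs and 41% with 14. Such an effect would miss significance in 68% and 59% of trials. The effect detectable with 80% power is 0.94 SD (11 pairs) or 0.81 SD (14 pairs). As an example, an observed difference of 1.0 with P = .12 has a 95% CI of −0.31 to 2.31 (11 pairs) or −0.30 to 2.30 (14 pairs).

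**6. Hypotheses against named tests.**

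| Hypothesis (section 1.5) | Values compared | Paired test usable? |
|---|---|---|
| 1. Serratiopeptidase add-on v conventional | Two sessions, same patients | Yes |
| 2. Escin add-on v conventional | Two sessions, same patients | Yes |
| 3. Serratiopeptidase v escin | Group I v group II patients | No, and no other test is named |

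**The case against.** Much of the other side's case on the reporting gap stands. A reader might infer that the treatment effect and its uncertainty are lost from the planned output. They are not: step 3 shows that means and an exact paired-t P give both back almost exactly. What remains is that the plan does not secure the conditions. It promises no exact P, it allows Wilcoxon, and it expects 20% drop-out across sessions three weeks apart.

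A reader might also infer that a non-significant result will be taken as no effect, or that the drugs will be ranked by their P values. Section 3.9 says nothing on either. Nor does it say that means, SDs and P are all that will be reported. Questions 1 and 2 ask whether each add-on is more effective, not by how much, so a significance test does address them as posed.

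The spread in step 2 could be made to look threefold by assuming equal SDs of 2 (half-widths 1.63, 1.15 and 0.52 at 14 pairs for ρ of 0, 0.5 and 0.9). That rests on assumed SDs and, like the twofold range, applies only if the P value is ignored.

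On hypothesis 3, it could be said that Wilcoxon's name is also attached to an unpaired rank-sum test. But section 3.9 offers it as the nonparametric counterpart of the paired t test, and the parametric branch would still lack a between-group test. It is fair to say that this gap is a missing analysis rather than a missing interval, and that filling it takes more than a change of wording.

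**Conclusion.** The point holds in two parts, and section 3.9 should be changed. The missing between-drug analysis weighs more, because it leaves hypothesis 3 without a method. The missing interval is a reporting weakness: the data would contain the answer, but the plan does not commit to showing it. With 11 to 14 pairs, the 95% CI extends 0.67 to 0.58 SD of the difference either side of a within-patient effect, and 0.89 to 0.78 SD for drug versus drug. A P of .05 or more would therefore not exclude a relevant effect.

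These SD-unit figures assume roughly normal differences, two-sided 5% testing and, for drug versus drug, the same SD of the difference in both groups. The figures in outcome units also depend on SDs borrowed from a rescue-analgesic outcome and on an assumed ρ. Reading the drug comparison as causal further assumes comparable groups: section 3.5 describes draws for tooth, intervention and order, but none for drug group.

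**What to change.** In section 3.9:

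- For each outcome and time point, report the mean within-patient difference (test minus control session) with its SD, 95% CI, exact P and number of complete pairs. Where Wilcoxon is used, report the Hodges–Lehmann estimate with its CI.
- For serratiopeptidase versus escin, compare the within-patient differences of group I with those of group II by an independent-samples analysis (two-sample t or Mann–Whitney). Report the difference of differences with its 95% CI.
- State that conclusions, including any of no difference, rest on the CI and not on P alone.

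The cost is one added between-group analysis and fuller reporting from the same data. Data collection and sample size do not change.

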1.4. Objectives of the study

Based on the above introduction and study question, the objectives can be classified into general and specific as follows:

General objective

The overall purpose of this study is to compare the efficacy of serratiopeptidase and escin in the reduction of post-operative complications (i.e., pain, trismus, and facial

swelling) following impacted third molar surgery, when both used in addition to conventional drugs.

Specific objective

1. Evaluate the efficacy of serratiopeptidase, when used in addition to conventional drugs, in reducing post-operative pain, trismus, and facial swelling following impacted third molar surgery.
2. Evaluate the efficacy of escin, when used in addition to conventional drugs, in reducing post-operative pain, trismus, and facial swelling following impacted third molar surgery.

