1.5. Study Hypotheses

Based on the study main problem, objectives, and literature review, three main hypotheses are constructed in order to test the relationship between the study variables.

These hypotheses are listed in this section as follows:

1. There is a statistically significant difference in serratiopeptidase, when used in addition to conventional drugs, in reducing post-operative pain, trismus, and facial swelling compared to conventional drugs alone following impacted third molar surgery.
2. There is a statistically significant difference in escin, when used in addition to conventional drugs, in reducing post-operative pain, trismus, and facial swelling compared to conventional drugs alone following impacted third molar surgery.
3. There is a statistically significant difference in serratiopeptidase in reducing post-operative pain, trismus, and facial swelling compared to escin, when

both used in addition to conventional drugs, following impacted third molar surgery.

Chapter 2:

Literature Review

2.1.Impacted Third Molar

The third molars, commonly known as wisdom teeth, often lead to complications during eruption, presenting a frequent concern in oral surgery (Wray et al., 2003). (Lytle, 1979) defines an impacted tooth as “*a tooth that has failed to erupt into its normal functional position beyond the time usually expected for such appearance. Eruption may have been prevented by adjacent hard or soft tissue including tooth, bone, or dense soft tissue*”. Among impacted teeth, mandibular third molars are the most common, followed by maxillary third molars and maxillary canines. Most unerupted teeth are extracted due to pain or infection, but other reasons include involvement in pathologies like cysts or tumors, causing resorption of adjacent teeth, or interfering with surgical procedures (Undrell Moore, 2011).

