3.1. Study Design

This clinical trial will utilize a split-mouth design, randomly assigning two different treatments to each half of the patient's mouth. From this randomized study which is characterized by a triple-blind study, the procedures are going to be performed by qualified and experienced professional. However, the operator will have no access to data evaluated. The evaluator will have access to all responses of the symptoms of patients and will not know the treatment that is going to be selected, while the patient is unaware of which treatment or intervention is being applied to each side of their mouth. This stringent blinding approach minimizes potential biases and significantly enhances the scientific validity of the study.

Patients will be assigned into two groups and each patient acted as their own control using the split-mouth technique. One impacted third molar will be removed from one side and will receive conventional drugs while the other side will be removed after 3 weeks (wash-out period) and receive additional treatment beside the conventional drugs (i.e., either enzyme or herbal). The two groups will be classified as follows:

- The first group will receive conventional drugs with 10mg oral serratiopeptidase at immediate post-operative time and three times a day for post-operative five days on the first surgical visit and on the second surgical visit (after 3 weeks) conventional drugs will be given only or vice versa.
- The second group will receive conventional drugs with 20mg oral escin at immediate post-operative time and three times a day for post-operative five days on the first surgical visit and on the second surgical visit (after 3 weeks) conventional drugs will be given only or vice versa.

The conventional drugs, it will be administered to patients in the two groups, includes: Amoxicillin 500mg Cap b.i.d., Metronidazole 500mg Tab t.i.d., Diclofenac sodium 50mg Tab b.i.d.

3.2.Study Population

The study population will include patients who will visit the dental clinics in the College of Dentistry, University of Science and Technology, Yemen (USTY) for impacted mandibular third molars extraction during 2024.

3.3.Sample Size

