3.5. Randomization

This clinical trial will utilize simple randomization based on the technique described by (Oliveira et al., 2021). This method involves drawing envelopes to determine the following:

- Surgical site: Test or control side
- Tooth: Right third molar ("A") or left third molar ("B")
- Surgery order: First or second session

The following steps of randomization will be followed:

1. Draw the tooth: An envelope is drawn to determine which third molar will be extracted first (right or left).
2. Draw the intervention: A second envelope is drawn to determine whether the selected tooth will receive the test intervention ("X-1") or no intervention ("X-2").
3. Draw the surgery order: A final envelope is drawn to determine whether the selected tooth will be extracted in the first or second surgery session.

3.6.Pre-operative and Post-operative Assessment

Prior to surgical removal of impacted third molar, preoperative variables (i.e., pain, trismus, and facial swelling) will be taken for each patient and recorded in the data collection sheet. Furthermore, the same post-operative variables (preoperative variables) will be taken immediately after the procedure, 2nd day, 3rd day and 5th day after the operation. Both pre-operative and post-operative variables will be done by the same measurements.

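### Section 3.9 names only paired tests, so serratiopeptidase versus escin (Hypothesis 3 and the general objective), a comparison of different patients, has no applicable test

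*Combined protocol and SAP*

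**What the plan says.** Section 3.9 is the whole statistical method. Pain, trismus and swelling are summarised as means and standard deviations and "compared using the paired t test (parametric) or Wilcoxon test (nonparametric"), with Shapiro–Wilk as the normality check and a .05 threshold. It does not say which test serves which hypothesis.

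The drug-versus-drug question appears in three places:

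- Section 1.2, question 3, asks "which one demonstrates superior efficacy in reducing post-operative pain, trismus, and facial swelling".
- Section 1.4, general objective: "The overall purpose of this study is to compare the efficacy of serratiopeptidase and escin in the reduction of post-operative complications".
- Section 1.5, Hypothesis 3: "There is a statistically significant difference in serratiopeptidase in reducing post-operative pain, trismus, and facial swelling compared to escin".

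On the design, Section 3.1 states: "Patients will be assigned into two groups and each patient acted as their own control using the split-mouth technique". One group gets serratiopeptidase at one surgery and the other group gets escin at one surgery. Each patient's other surgery is covered by conventional drugs alone. Table 3-1 in Section 3.3 puts 14 patients in each group, and the text adds: "This will result in a total sample size of 56 dental units (2 teeth per patient) from 28 patients". Section 3.5 draws the tooth, the intervention and the surgery order. On the intervention it says: "A second envelope is drawn to determine whether the selected tooth will receive the test intervention". It describes no draw between Group I and Group II.

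**The concern.** A paired test needs two observations that belong together. For Hypotheses 1 and 2 the patient provides them. For Hypothesis 3 a Group I patient has no partner in Group II, so the stated rule does not apply.

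The comparison that the plan calls its overall purpose therefore has no pre-specified analysis. The test, and the quantity it compares (raw values, changes or study-minus-control differences), would be settled once results are visible. There are three outcomes, three swelling lines and four post-operative assessments to choose among.

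Two workarounds could be read into the wording. One pairs unrelated patients by list position. The other compares the two within-group p-values, which does not test Hypothesis 3 and could name a superior drug when both work equally well.

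**Working it through.** **1. Match each hypothesis to the stated test.**

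| Comparison | Who supplies the data | Does Section 3.9 fit? |
|---|---|---|
| Hypothesis 1: serratiopeptidase + conventional v conventional | Same 14 patients (Group I) | Yes |
| Hypothesis 2: escin + conventional v conventional | Same 14 patients (Group II) | Yes |
| Hypothesis 3: serratiopeptidase v escin | 14 patients v 14 other patients | No |

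No section names an independent-samples t test, rank-sum test, ANOVA, ANCOVA or mixed model.

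**2. Reproduce the plan's sample size.** Inputs from Section 3.3: means 1.6 and 4.0 (difference 2.4), SDs 1.3 and 2.5, 80% power, 95% confidence (taken as two-sided 5%).

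n = (1.3² + 2.5²)(1.960 + 0.842)² / 2.4² = 10.82, rounded up to 11. With 20% drop-out, 11/0.8 = 13.75, rounded up to 14. Both stated figures reproduce. The calculation is for an active drug against placebo and has no input for serratiopeptidase versus escin.

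**3. Workaround A: pair unrelated patients.** Simulation with normal data, 14 v 14, 200,000 runs:

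- Type I error is 5.0%, the same as the two-sample test.
- Degrees of freedom fall from 26 to 13, and the critical t rises from 2.06 to 2.16.
- Power at a 1.1 SD difference is 76.8%, against 80.1% for the two-sample test.
- The p-value depends on list order. In 300 data sets fixed at a two-sample p of 0.05, with 2,000 orderings each, the median 2.5th and 97.5th percentiles of the paired p were 0.011 and 0.119.

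**4. Workaround B: see which paired test is significant.** The groups are independent. If both drugs work equally well and each paired test has power p, exactly one is significant with probability 2p(1 − p). At p = 0.80 this is 2 × 0.80 × 0.20 = 32%.

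With the Section 3.3 inputs, the SD of the paired difference is √(1.3² + 2.5² − 2ρ × 1.3 × 2.5) = √(7.94 − 6.5ρ). The within-patient correlation ρ is not in the documents and is assumed. Power is from the noncentral t, two-sided 5%.

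| ρ (assumed) | SD of difference | Power, 14 pairs | Exactly one significant | Power, 11 pairs | Exactly one significant |
|---|---|---|---|---|---|
| 0 | 2.82 | 83.8% | 27.2% | 72.1% | 40.2% |
| 0.3 | 2.45 | 92.3% | 14.2% | 83.4% | 27.7% |
| 0.5 | 2.17 | 96.9% | 6.0% | 91.1% | 16.3% |
| 0.7 | 1.84 | 99.4% | 1.1% | 97.3% | 5.3% |

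**5. What a proper between-group test can detect.** For a two-sample t test on the within-patient differences, 80% power needs 1.10 SD with 14 per group or 1.26 SD with 11. In Section 3.3 units:

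| ρ (assumed) | 14 per group | 11 per group |
|---|---|---|
| 0 | 3.10 | 3.54 |
| 0.3 | 2.69 | 3.07 |
| 0.5 | 2.38 | 2.72 |
| 0.7 | 2.03 | 2.31 |

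Against the 2.4 used for sizing, that is 84% to 129% with 14 per group and 96% to 147% with 11.

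**6. Why a mixed model must keep the two control sub-groups apart.** Suppose the groups differ by 1 unit at patient level on both sides. Before baseline adjustment, a model with no group term lets 1 − ρ of that into the drug contrast: 0.70, 0.50 and 0.30 at ρ = 0.3, 0.5 and 0.7. With a group term, none enters.

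**The case against.** Five points can be made for the plan.

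- **The Wilcoxon test is not qualified and could mean rank-sum.** It is offered as the nonparametric counterpart of the paired t test, so signed-rank is the natural reading. Even as rank-sum, normally distributed data would have no between-group test and the quantity compared would be undefined.
- **No passage proposes either workaround, and pairing unrelated patients does little harm on average.** This stands. It keeps 5% type I error and costs about three points of power. The workaround figures show what the gap permits, not what the trial intends.
- **The figures borrow rescue-analgesic data from an etoricoxib trial and assume correlations.** This also stands. Rescue-analgesic use is not among this trial's assessed outcomes, and the 1% to 40% range is driven mainly by ρ and n. The finding rests on the missing test, not on these numbers.
- **The two-sample t test ignores session, while the mixed model includes it.** This is correct. Because treatment order is drawn at random, omitting session adds noise to the contrast, not bias.
- **Hypotheses 1 and 2 and both specific objectives have a suitable test, and no data are lost.** This is also true. But Section 1.4 makes the drug-versus-drug comparison the general objective, so the gap is not a side issue.

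**Conclusion.** The concern holds and must be fixed. As written, Section 3.9 cannot test Hypothesis 3 or the general objective, because serratiopeptidase and escin are given to different patients and only paired tests are specified. This conclusion needs no numerical assumption beyond reading the Wilcoxon test as signed-rank, and the alternative reading leaves most of the gap open.

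The consequence depends on what the analyst does. Ranking equally effective drugs by paired significance would split them 32% of the time at 80% power each. With the Section 3.3 inputs the figure runs from 1% to 27% with 14 pairs and from 5% to 40% with 11, for assumed correlations of 0.7 down to 0. These are illustrations for pain, trismus and swelling, since the inputs concern a different outcome.

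**What to change.** In Section 3.9:

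- Keep the paired tests for Hypotheses 1 and 2, and name the Wilcoxon test there as signed-rank.
- For Hypothesis 3, compute each patient's study-side minus control-side difference in change from the pre-operative value. Compare Group I with Group II by an independent two-sample t test, with rank-sum as fallback, and report a 95% confidence interval.
- Name in advance the post-operative time point or points, and the rule for combining the three swelling lines.
- If a mixed model is preferred, include group (so that Control 1 and Control 2 stay separate), condition, group-by-condition, session and pre-operative value, with a random patient effect. Hypothesis 3 is the group-by-condition term.
- State that comparing the two paired p-values is not a test of Hypothesis 3.
- State that at this sample size only large between-drug differences are detectable, giving the figures for both 14 and 11 per group.

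In Section 3.5, describe how patients are allocated between Group I and Group II. Unless a random draw is added, word Hypothesis 3 conclusions as a comparison of groups whose random allocation is not described.

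The test itself costs only wording, because group, sub-group, visit and pre-operative values are already on the case sheet in Appendix A. The real cost is admitting that the headline comparison has 80% power only for differences of about 1.10 SD (14 per group) or 1.26 SD (11 per group). Adding a draw between the groups would be a change to the randomization procedure.
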